9.7.1.6.4. Dilated Ophthalmoscopy

The frequency and percentage of subjects with observed values of each categorical response at Visits 1 and 6 as well as the categorical shift from baseline at Visit 6 will be tabulated for both eyes. The percentages are calculated based on the number of subjects at each visit in each treatment group of the Safety Analysis Set.

Descriptive summaries of the observed cup-to-disc ratio at Visits 1 and 6 as well as the change from baseline at Visit 6 will be presented for both eyes.

9.7.1.6.5. Heart Rate and Blood Pressure

Descriptive summaries of the observed values for heart rate and blood pressure at each scheduled visit as well as the change from baseline at each post-baseline visit will be presented.

Repeat measurements of cardiovascular outcomes will be taken for out-of-range measurements. The most recent (latest measurement) at each visit will be summarized in tables.

9.7.1.6.6. Clinical Laboratory Tests (Blood Chemistry, Hematology)

Descriptive summaries of the observed test results at Visits 1 and 6 as well as the change from baseline at Visit 6 will be presented for blood chemistry and hematology labs. The frequency and percentage of subjects with observed values of Low, Normal, High at baseline and Visit 6 will be tabulated. The percentages are calculated based on the number of subjects at each visit in each treatment group of the Safety Analysis Set.

It is expected that all samples will be analyzed by a central laboratory. If a local laboratory is used (such as for an unscheduled visit), the results will be included in the listings of laboratory data, but will not be included in descriptive summaries.

The results of pregnancy tests for women of childbearing potential will be presented in a listing.

9.7.2. Determination of Sample Size

With a sample size in each group of 20, the study will have 80% power to detect a difference of 3.0 mmHg between an VVN539 dose compared to vehicle at each diurnal time point assuming a common standard deviation of 3.3 mmHg, $\alpha = 0.05$ (two-tailed).

There is no correction for multiplicity for multiple time points or comparisons for high or low VVN539 doses.

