9.5.1.3.3. Description of Efficacy Assessments

IOP measurements will be performed utilizing a Goldmann applanation tonometer affixed to a slit lamp according to the Investigator's standard procedure (two-person reading method). Measurements will be taken with the subject seated. All pressure will be recorded in mmHg. Two consecutive measurements are taken in each eye and recorded as the mean of the two measurements. If the two measurements differ by >1.0 mmHg, a third measurement is performed, and the median is recorded.

At Visit 1, IOP will be measured once during screening visit.

At Visit 3, IOP will be measured once at 8:00AM (± 30 minutes) prior to the first q.d. AM dosing.

At Visits 2, 4, 5, and 6 diurnal IOP will be measured:

- At 8:00AM (± 30 minutes), 10:00AM (± 30 minutes) and 4:00PM (± 30 minutes)
- At Visits 4 and 6, the 8:00AM measurement will be taken prior to the AM dosing.

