9.5.3. Primary Efficacy Variable(s)

The primary efficacy endpoint for this study is to compare mean IOP at each diurnal time point (8AM, 10AM, and 4PM) at Visit 4 (Day 7), Visit 5 (Day 14), and Visit 6 (Day 21) for two doses of VVN539 compared to vehicle using data from the study eye.

To claim superiority, the two-sided 95% confidence interval estimates of the treatment differences in mean IOP between VVN539 and vehicle must exclude zero for all 9 time points.

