For analysis of efficacy endpoints, analysis of covariance (ANCOVA) or longitudinal models will model the observed value or change from baseline of each endpoint as the dependent variable with the baseline measurement of the corresponding endpoint as a covariate and treatment group as a main effect. Longitudinal models will include a covariate for visit as well as an interaction term for visit and treatment.

Subgroups

Not applicable.

Multiplicity

Time-matched longitudinal models adjusting for baseline and including a random effect for center will be used to test time-specific superiority comparisons as well as the overall superiority hypothesis using 95% confidence intervals. To claim study success for the primary endpoint based on the model, the two-sided 95% confidence interval estimates of the treatment differences in mean IOP between VVN539 and vehicle must exclude zero for all 9 time points (8AM, 10AM, and 4PM at Visits 4, 5, and 6). No adjustment to the individual confidence intervals is required since all criteria need to be met to claim superiority.

Comparisons will be made first between VVN539, 0.04% versus vehicle. If the treatment differences for all 9 time points are statistically significant, testing will proceed to VVN539, 0.02% versus vehicle.

Missing Data and Outliers

Every attempt will be made to capture all study data. The primary analysis will be analyzed using observed data assuming missing at random (MAR) using a longitudinal model (mixed model repeated measures, MMRM). Sensitivity analyses of the primary endpoint will be performed utilizing time-matched last observation carried forward (LOCF) of the last available IOP measurement.

Safety analyses will use observed data only.

Visit Windows

The nominal visits listed in the CRF will be used in the summaries. In general, unscheduled visits will not be summarized in tables unless otherwise noted.

Missing Dates

Missing dates that occur for prior or concomitant medications or adverse events will be queried for a date. If no date is obtained, the following imputation rules will apply:

- For start dates, if the given year (or year-month) is the same as study drug administration, the start date will be imputed as study drug administration date; otherwise, missing month-day (or day) will be imputed as '01-01' (or '01').

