9.7.1.5.1. Primary Efficacy Analysis

Primary Estimands: The primary estimands are the treatment differences between VVN539 and vehicle at 8:00 AM, 10:00 AM, and 4:00 PM at each of Days 7, 14, and 21 in the study eye using the FAS. The primary estimands treat subjects as if they do not receive rescue therapy.

Target Population: Subjects with open-angle glaucoma or ocular hypertension that meet the study entry criteria.

Endpoint: Observed IOP measurements at each time point in the study eye.

Treatment Condition(s): Treatment condition is based on the randomized treatment group.

Population-level Summaries: The difference in the mean IOP at the nine time points of interest and their corresponding p-values and 95% confidence intervals.

Intercurrent Events and Strategies to Address Intercurrent Events

- Discontinuation of study therapy with continued participation in the study without receipt of rescue therapy
 - Treatment Policy – no imputation; use observed data
- Receipt of rescue therapy in the study eye
 - Hypothetical Approach – data for visits after the receipt of rescue therapy will be set to missing and will be analyzed assuming missing at random (MAR) using a longitudinal model (mixed model repeated measures, MMRM)
- Missing data without withdrawal or with withdrawal regardless of reason
 - Hypothetical Approach: visits that are missing data will be analyzed assuming MAR using MMRM

Time-matched longitudinal models adjusting for baseline and including a random effect for center will be used to test time-specific superiority comparisons as well as the overall superiority hypothesis using 95% confidence intervals. To claim study success for the primary endpoint based on the model, the two-sided 95% confidence interval estimates of the treatment differences in mean IOP between VVN539 and vehicle must exclude zero for all 9 time points (8AM, 10AM, and 4PM at Visits 4, 5, and 6). Comparisons will be made first between VVN539, 0.04% versus vehicle. If the treatment differences for all 9 time points are statistically significant, testing will proceed to VVN539, 0.02% versus vehicle.

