Data from Days 7, 14, and 21 will be analyzed using MMRM with an unstructured covariance assumed for each treatment with treatment, visit, and visit by treatment interaction as a fixed effects, baseline measurement as a covariate, and a random effect for site. If the model fails to converge using this covariance structure, heterogenous Toeplitz, or compound symmetry will be implemented in this order until convergence is reached.

Sample code for the model run separately for 8AM, 10 AM, and 4 PM:

```
PROC MIXED DATA=indata;
  CLASS subject site visit treatment;
  MODEL IOP = baseline visit treatment visit*treatment / solution DDFM=KR;
  REPEATED visit / SUBJECT=subject TYPE=UN group = treatment;
  RANDOM site;
  LSMEANS visit*treatment / slice = visit CL diff;
RUN;
```

Sensitivity analyses include a time-matched last observation carried forward (LOCF) of the last available IOP measurement as well as analysis of covariance (ANCOVA) analyses at each visit with baseline measurement as a covariate. Percent of baseline and percent change from baseline

will also be performed as a sensitivity of the primary analysis. Additional sensitivity analyses will be performed on the PP Analysis Set as necessary.

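### Is 20 per arm underpowered because the stated 80% covers one time point while the success rule needs all nine?

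*SAP*

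**What the plan says.** SAP 9.7.2, like protocol 9.2, bases 20 per group on "80% power to detect a difference of 3.0 mmHg between an VVN539 dose compared to vehicle at each diurnal time point". The SD is 3.3 mmHg and alpha is 0.05 two-sided. Neither section says whether the SD is before or after baseline adjustment, and neither gives a correlation between readings.

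The decision rule stands elsewhere in the SAP. Section 9.5.3 requires that the 95% intervals for the differences "between VVN539 and vehicle must exclude zero for all 9 time points". The Multiplicity paragraph of 9.7.1 adds: "No adjustment to the individual confidence intervals is required since all criteria need to be met to claim superiority". On the doses, 9.7.1.5.1 says "Comparisons will be made first between VVN539, 0.04% versus vehicle", and 9.7.1 continues: "If the treatment differences for all 9 time points are statistically significant, testing will proceed to VVN539, 0.02% versus vehicle".

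The primary model in 9.7.1.5.1 has "baseline measurement as a covariate, and a random effect for site" and is run separately for 8AM, 10AM and 4PM. The same section lists what is reported: "The difference in the mean IOP at the nine time points of interest and their corresponding p-values and 95% confidence intervals".

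**The concern.** The sample size is argued for one comparison, while the study claim needs nine at once. One interval that includes zero for 0.04% defeats the claim and ends formal testing of 0.02%. Winning nine times together is harder than winning once, so a reader who takes 80% as the chance of study success may be misled. A missed claim could then be read as lack of effect when it was a likely outcome at this sample size.

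The text also suggests how this arose. The protocol states its hypotheses by time point (9.1) and contains no nine-point success rule. The SAP adds the rule and the dose order but keeps the protocol's sample-size text, including its remark that multiplicity is not corrected. SAP 9.8.2 does not list the rule among the changes.

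**Working it through.** **Inputs.** From SAP 9.7.2: n = 20 per arm, difference 3.0 mmHg, SD 3.3 mmHg, alpha 0.05 two-sided. From protocol 5.1.2: 1:1:1 allocation. Assumed, because the documents give no values: correlation between readings 0.3 to 0.8, share of variance removed by baseline 0% to 50%, a true 3.0 mmHg at all nine points, and complete data.

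**1. The plan's own figure.** The standard error is 3.3 × √(2/20) = 1.044. The noncentrality is 3.0/1.044 = 2.875. With 38 degrees of freedom the critical value is 2.024, and the noncentral t gives power 0.79997. The stated 80% is reproduced.

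**2. Bounds, if 3.3 mmHg is the SD of the analysed quantity.** All nine cannot succeed more often than any one of them, so the ceiling is 80%. Under independence the power is 0.8^9 = 0.134.

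**3. Baseline adjustment, if 3.3 mmHg is raw.** The adjusted SD is 3.3 × √(1 − share removed):

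- 25%: 3.3 × √0.75 = 2.858, single-point power 0.899
- 40%: 3.3 × √0.60 = 2.556, single-point power 0.951
- 50%: 3.3 × √0.50 = 2.333, single-point power 0.977

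**4. Power for all nine.** Three arms sharing one vehicle group, nine correlated normal readings with a common residual correlation, a t-test at each point with the SD above (standing in for the mixed model), and 40,000 trials per case:

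| Variance removed | 0.04% wins all nine, correlation 0.3 / 0.5 / 0.8 | Both doses win | Difference with 80% all-nine power (mmHg) |
|---|---|---|---|
| 0% (3.3 is adjusted) | 0.295 / 0.398 / 0.569 | 0.138 / 0.226 / 0.403 | 4.10 / 3.98 / 3.66 |
| 25% | 0.522 / 0.605 / 0.739 | 0.336 / 0.436 / 0.604 | 3.55 / 3.44 / 3.17 |
| 40% | 0.714 / 0.766 / 0.854 | 0.556 / 0.635 / 0.763 | 3.17 / 3.08 / 2.83 |
| 50% | 0.846 / 0.874 / 0.922 | 0.741 / 0.791 / 0.868 | 2.90 / 2.81 / 2.59 |

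Power reaches 80% when baseline removes about 46%, 43% or 33% of the variance at residual correlations of 0.3, 0.5 or 0.8.

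**5. Time-matched baselines.** Each clock time has its own model and its own baseline. If all readings, baseline included, share one correlation ρ, the residual correlation is ρ/(1+ρ) within a clock time and ρ(1−ρ)/(1+ρ) between clock times. At ρ = 0.7 these are 0.7/1.7 = 0.41 and 0.7 × 0.3/1.7 = 0.12. Simulated per-visit ANCOVA on this structure, with 3.3 mmHg raw, gives all-nine power of about 27%, 44%, 62%, 80% and 97% at ρ = 0.3, 0.5, 0.6, 0.7 and 0.8, to within a point or two. Treating all nine readings as sharing a single baseline would give 32%, 53%, 68%, 85% and 97%, which is too high in the middle of the range.

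**6. Departures go both ways.** Of the 8AM readings, those at two of the three visits precede the morning dose ("At Visits 4 and 6, the 8:00AM measurement will be taken prior to the AM dosing"). If the 8AM effect is 2.5 mmHg (assumed), the first row of the table falls to 20-46%. If the effect is 3.0 mmHg at 8AM and 3.5 mmHg at the other six points (assumed), it rises to 42-66%. With 18 per arm (assumed) it falls to 22-51%.

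**7. Error control.** A false claim for a dose needs all nine intervals to exclude zero, so it is no more likely than the error at any one point whose null is true. The second dose is tested only after the first has succeeded. No interval needs adjusting, as 9.7.1 says. The remark in 9.7.2 that nothing is corrected agrees with this: every interval stays at 95%, and an analyst takes the dose order from 9.7.1 and 9.7.1.5.1.

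**The case for a change.** The strongest case for a change is that the rule deciding the headline claim has no power on record. If 3.3 mmHg is the analysed SD, a shortfall below 80% is certain at any correlation below 1. The remedy would be cheap: label the 80%, state the basis of the SD, and add a short simulation.

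The facts in this stand; the consequence does not. The label is largely there already, since the sentence speaks of one dose against vehicle at each time point and promises nothing about study success. The simulation would rest on correlations and a variance share that the documents do not supply, and its answer would run from about 27% to 97% according to the choice made. The one response that could alter a result is a larger trial. If 3.3 mmHg is the adjusted SD, about 37, 35 or 30 per arm would be needed at correlations 0.3, 0.5 or 0.8. The documents do not establish that reading, and if baseline removes half of a raw variance, 20 per arm already exceeds 80%. The risk of misreading a missed claim is limited, because all nine differences appear with their intervals whatever the claim.

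**Conclusion.** The mismatch is real, but it is missing detail rather than a defect. The SAP delivers the power it states, and no figure in it is wrong. All-nine power for 0.04% is about 30-57% on the less favourable reading of the SD and about 52-92% if it is raw and baseline removes 25-50% of the variance. These figures rest on assumed correlations of 0.3 to 0.8, a uniform 3.0 mmHg and complete data. Which side of 80% applies cannot be settled from the documents.

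Requiring all nine points is a fair trade-off in a first-in-human phase 2 dose-response study: it controls type I error without splitting alpha, at a cost in power. A power figure for the rule would be useful background for a reader. Adding it would not alter enrolment, the model, error control, any estimate or any conclusion, so no change to the plan is called for.

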9.8. CHANGES IN THE CONDUCT OF THE STUDY OR PLANNED ANALYSES

9.8.1. Protocol Amendments

Amendment 1 of protocol made the following notable changes:

- Revised exclusion criteria to minimize the risk of study subjects randomized to vehicle for potential glaucomatous loss;
- Allowed investigators to switch subjects who were previously treated with an ocular hypotensive medication with a 4 week washout period to a ocular hypotensive medication with a shorter washout period provided the appropriate washout is met prior to Visit 2.

9.8.2. Changes from Protocol-Specified Analyses

Version 2 of the statistical analysis plan clarifies the inconsistent presentation of analyses with regards to rescue and prohibited medications. This version clarifies that data prior to rescue treatment will be used for efficacy analyses. Minor corrections to sample proc mixed code were made as well.

REFERENCES

1. Mozzicato P. (2009). MedDRA: An overview of the medical dictionary for regulatory activities. *Pharmaceutical Medicine* 23: 65-75.
3. SAS Institute Inc. What's New in Base SAS® 9.4 and SAS® Viya®. (2013). SAS Institute Inc., Cary, NC, USA.
4. SAS Institute Inc. (2020). SAS/STAT User's Guide. SAS Institute Inc., Cary, NC, USA.

APPENDIX I: SCHEDULE OF ASSESSMENTS

Table 1: Schedule of Assessments

Study Period	Screening	Washout ¹	Baseline	Treatment Period				End of Treatment
				2	3	4	5	
Visit No.	1		2	Day 0	Day 1	Day 7 (+2)	Day 14 (+2)	6
Visit Window	Day-35 to -1							Day 21 (+2)
Informed consent ²	X							
Ocular and medical history	X		X					
Demographics	X							
Inclusion/Exclusion criteria	X		X					
BCVA	X			X	X	X	X	X
Biomicroscopy ³	X			X	X	X	X	X
IOP	X				X ⁴			
Diurnal IOP ⁵			X			X	X	X
Cup-to-disc ratio	X							X
Dilated ophthalmoscopy	X							X ⁶
Pachymetry ⁷	X							X
Gonioscopy ⁸	X							

¹ Washout period: Prostaglandins, β -adrenoceptor antagonists, kinase inhibitors (4 weeks), adrenergic agonists (2 weeks), muscarinic agonists and carbonic anhydrase inhibitors (5 days)

² Informed consent will be obtained prior to the conduct of any study specified or associated procedures or evaluations.

³ Biomicroscopy of anterior segment includes corneal epithelium, bulbar and lower conjunctiva, and lens.

⁴ Measured at 8:00AM

⁵ Measured at 8:00AM, 10:00AM and 4:00PM

⁶ After the last IOP measurement

⁷ Central corneal thickness will be measured at entry for IOP interpretation. Pachymetry performed within 3 months of screening is acceptable. Ultrasound and optical pachymetry is permissible provided that the same methodology is used at Visits 1 and 6.

⁸ Gonioscopy performed within 3 months of Visit 1 is acceptable.

Study Period	Screening	Washout ¹	Baseline	Treatment Period			End of Treatment
Visit No.	1		2	3	4	5	6
Visit Window	Day-35 to -1		Day 0	Day 1	Day 7 (+2)	Day 14 (+2)	Day 21 (+2)
Visual field ⁹	X						
Optical Coherence Tomography	X ¹⁰						
Blood chemistry, hematology	X						X
BP, HR	X		X	X	X	X	X
Pregnancy test ¹¹	X		X				X
Randomization			X				
Study drug administration in clinic				X ¹²	X ¹³		X ¹³
Dispense investigational product				X	X	X	
Collect study drug					X	X	X
Prior/Concomitant medications	X		X	X	X	X	X
Adverse event assessment			X	X	X	X	X

Abbreviation key: BCVA=best corrected visual acuity; BP=blood pressure; HR=heart rate; IOP=intraocular pressure

⁹ Visual field within 3 months of Visit 1 is acceptable, provided that it is reliable and meets the requirement for automated threshold visual field (e.g., 30-2 or 24-2 Humphrey). Unreliable entry fields must be repeated prior to study drug dispensation.

¹⁰ Optical Coherence Tomography within 3 months of Visit 1 is acceptable.

¹¹ Women of childbearing potential only

¹² After 8:00AM IOP measurement

¹³ After 8:00AM and prior to 10:00AM IOP measurement
